5.3 Final Analysis Plan

An objective of this study is to investigate the influence of heat application on the PK parameters of rivastigmine after using a RLD or generic TDS. The primary PK parameters

to be compared are 1) C_{max} , before and after heat application; 2) AUC before and after heat application consistent with similar PK studies^(6,7). Determine PK parameters (C_{max} , AUC) of rivastigmine in healthy adults after using Exelon® and rivastigmine generic TDS for the purpose of IVIVC by collecting data. Complimentary in vitro data will be collected using human skin.

IVIVC will be conducted comparing PK parameters and profiles to predicted PK parameters and profiles using IVPT results. Multiple methods will be implemented to develop an IVIVC. The first method is to compare the steady state concentrations. The predicted steady state concentration using our current IVPT data will employ the following formula:

$$C_{ss} = \frac{J_{ss} * A}{CL}$$

C_{ss} =steady state serum concentration; J_{ss} =steady state flux; A=area; CL=clearance

The second method will compare the PK profiles of the clinical and IVPT study by predicting rivastigmine concentrations at each time point in the IVPT study and comparing it to the PK profile. The third method will be to determine and compare residual TDS analysis between in vitro and in vivo.

Intra-procedure comparisons:

For Study Session 1-4:

- C_{max} will be compared among the following time periods: 0-5 h, 5 h-6 h 30 min, 6 h 30 min-9 h and 9-12 h post TDS application
- AUC: will be compared among the following time periods: 0-5 h, 5 h-6 h 30 min, 6 h 30 min-9 h and 9-12 h post TDS application

Inter-procedure comparisons:

For Study Session 1-4: Both C_{max} and AUC will be compared among procedure groups for the following time periods: 5 h -6 h 30 min.

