Description of Study Design:	
The study will be an open-label, crossover study (n=12 healthy subjects) over ~10 weeks includes four study sessions with up to a 45 day screening period with one week washout period between study sessions.
 
The study contains four study sessions:
 
• Study Session 1: Exelon[®] TDS containing 9 mg (4.6 mg/24 h) of rivastigmine base to be worn for ~9 h.• Study Session 2: Rivastigmine generic TDS containing 6.9 mg (4.6 mg/24 h) of rivastigmine base to be worn for ~9 h.• Study Session 3: Exelon[®] TDS containing 9 mg (4.6 mg/24 h) of rivastigmine base to be worn for ~9 h. The heating pad will be set to induce a skin temperature of 42.0 ± 4°C and applied for 1 hour 30 minutes at 5 h after application of the TDS.

Study Session 4: Rivastigmine generic TDS containing 6.9 mg (4.6 mg/24 h) of rivastigmine base to be worn for ~9 h. The heating pad will be set to induce a skin temperature of $42.0 \pm 4^\circ\text{C}$ and applied for 1 hour 30 minutes at 5 h after application of the TDS.

A) Pharmacokinetics (PK)

Each subject will be his/her own control (pre-dose blood sample) and each subject will sign an institutional review board–approved consent form explaining the purpose, nature, risks, benefits, and duration of the study. The study will be conducted in accordance with good clinical practice guidelines and with the ethical principles originating in the Declaration of Helsinki.

The subject's skin in the area of application (upper arm) will be relatively free of hair before TDS application. Blood samples (approximately 4 mL each) will be drawn in BD vacutainer tubes. Blood samples will be obtained as follows:

- Within 60 min pre-application and then up to ~12 h after TDS application.

B) Residual Drug Analysis of Rivastigmine TDS

In conjunction with the above described study, residual drug analysis will also be conducted for the previously worn Exelon® and rivastigmine generic TDS from Study Session 1-4.

- Prior to administration to the subject as described in Part A, TDS will be weighed and the weight recorded.
- The pouch, release liner and all items coming into contact with the TDS (gloves, forceps, etc..) applied in Part A will be retained for analysis.
- The used TDS will be retained for drug content analysis.
- All items coming into contact with the TDS during removal from the subject will be stored in a separate labeled sealable pouch until analyzed for drug content.

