2.2 Rationale

The goal of this study is to conduct in vivo studies to compare the influence of heat on rivastigmine drug permeation from FDA approved products; Exelon[®] TDS versus rivastigmine generic TDS. While there is data in the literature for heat effect on different active pharmaceutical ingredients (APIs), specifically RLD products, from exposure to external heating sources (heating pads, sauna, hot showers, exercising), there is no head-to-head comparisons for heat effect on RLD versus generic during application. Therefore, to help ensure that TDS are safe for patients, an in vitro setup is being developed to characterize the heat effect for these systems by correlating the in vivo data with in vitro data using the IVPT model with excised human skin. This necessitates that a small number of human subject heat effect studies are performed under controlled and monitored conditions with selected products, to serve as an in vivo reference for parallel IVPT heat effect studies. The rivastigmine heat effect studies described in this protocol are the final set in this series of studies. The intent of this research is to establish an IVVC for the IVPT model in the specific context of heat effect studies, so that IVPT studies can be utilized to

evaluate whether all future generic products are similar in quality to the RLD in terms of heat effect. In addition, the residual drug content of the used rivastigmine TDSs will be analyzed for the purpose of estimating the amount of drug absorbed.

Rivastigmine Products

Properties	Exelon TDS	Alvogen TDS									
Excipients	Acrylic copolymer, poly(butylmethacrylate, methylmethacrylate), silicone adhesive applied to a flexible polymer backing film, silicone oil and vitamin E	Colloidal silicon dioxide, light mineral oil, polyisobutylene adhesive, acrylate-vinylacetate pressure sensitive adhesive, aluminum coated polyester backing									
Drug load	9 mg	6.9 mg									
Delivery rate	4.6 mg/24 h (0.19 mg/h)	4.6 mg/24 h (0.19 mg/h)									
Size	5 cm ²	4.6 cm ²									
Manufacturer	LTS Lohmann Therapie-Systeme AG	Alvogen, Inc									
Distributor	Novartis Pharmaceuticals Corp.	Alvogen, Inc									

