3.2 Study Outcome Measures

For the PK study the main outcome measure is the maximum serum concentration (C_{max}); time of maximum serum concentration (T_{max}) of rivastigmine and area under the curve (AUC) attained with and without heating for Exelon® TDS and rivastigmine generic TDS. In addition, we will determine residual drug content from worn TDSs to estimate total amount of absorbed rivastigmine.

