5 PHARMACOKINETICS AND STATISTICAL CONSIDERATIONS

5.1 Analyses

Rivastigmine concentrations will be measured in serum samples collected from each subject. Blood samples (approximately 4 mL or 5 mL (~1 tsp)) will be collected within 60 min of pre-application and then at 2 h, 3 h, 4 h, 5 h, 5 h 15 min, 5 h 30 min, 5 h 45 min, 6 h, 6 h 15 min, 6 h 30 min, 7 h, 7 h 30 min, 8 h, 8 h 30 min, 9 h, 9 h 15 min, 9 h 30 min, 10 h, 11 h and 12 h post-TDS application.

Non compartmental analyses (NCA) will be conducted to estimate the PK parameters such as: maximum serum concentration (C_{max}), apparent elimination rate constant (k); apparent half-life ($t_{1/2}$), calculated as $0.693/k$; AUC_{0-last} of the serum concentration–time determined by the linear trapezoidal method (TDS); and AUC value extrapolated to infinity (AUC_{inf}), calculated as the sum of AUC_{0-last} and the area extrapolated to infinity: $AUC_{inf} = AUC_{0-last} + C_{last}/k$ where C_{last} would be the last quantifiable concentration. All NCA analyses will be conducted using Phoenix[®] WinNonlin[®] 6.4 (Pharsight, a Certara Company, CA).

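### Section 5.3 makes before versus after heat the primary comparison, which confounds heat with time since application; the heated-versus-unheated contrast is not designated primary and no heat-by-product contrast is written

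*Combined protocol and SAP*

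**What the plan says.** Section 5.3 uses the word primary once, for C_max "before and after heat application; 2) AUC before and after heat application consistent with similar PK studies". By the Protocol Summary, the heating pad is used only in Sessions 3 and 4, "applied for 1 hour 30 minutes at 5 h after application of the TDS".

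Section 5.3 then lists two sets of comparisons:

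- Intra-procedure, for each of Sessions 1–4: C_max across four windows, and likewise "AUC: will be compared among the following time periods: 0-5 h, 5 h-6 h 30 min, 6 h 30 min-9 h and 9-12 h".
- Inter-procedure: both parameters "will be compared among procedure groups for the following time periods: 5 h -6 h 30 min".

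Section 3.2 words the main outcome differently, as C_max, T_max and AUC "attained with and without heating for Exelon® TDS and rivastigmine generic TDS". Section 2.2 gives the study's goal as to "compare the influence of heat on rivastigmine drug permeation from FDA approved products", reference product versus generic.

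The plan names no statistical test and does not say which comparison decides if they disagree.

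**The concern.** Before and after heat are different times since the patch was applied. Any rise or fall in concentration around 5 h is therefore counted as a heat effect. The documents give no lag, T_max or half-life to show that the profile is flat by then.

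Two features of the plan add to this. C_max is a maximum, and the heat window holds more samples than the window before it. The AUC windows also differ in length.

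Section 3.2 points to a different contrast, heated session against unheated session, so the two sections do not define the same primary quantity.

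The product question has its own gap. If the two products differ in absorption lag, their before/after changes differ even when heat does nothing. A direct Session 4 versus Session 3 comparison carries any baseline difference in exposure between products. Neither isolates a difference in heat effect.

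**Working it through.** **1. The plan's only power figure.** Section 5.2 uses AUC over 24 h of 166 ± 50, an error of 25% and n = 12. Power = Φ(√12 × 0.25/(50/166) − 1.960) = Φ(2.875 − 1.960) = Φ(0.915) = 82%. This reproduces as a two-sided 5% calculation. It concerns one AUC in one condition, so it says nothing about any heat contrast.

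**2. Samples per window.** Section 5.1 gives a pre-dose sample, then "2 h, 3 h, 4 h, 5 h, 5 h 15 min, 5 h 30 min, 5 h 45 min, 6 h", then 6 h 15 min, 6 h 30 min and onwards to 12 h.

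| Window | Length | Samples, both ends counted |
|---|---|---|
| 0–5 h | 5 h | 5 (4 post-dose) |
| 5–6.5 h | 1.5 h | 7 (6 after heat starts) |
| 6.5–9 h | 2.5 h | 6 |
| 9–12 h | 3 h | 6 |

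**3. AUC by hand, no heat effect.** Take a profile that rises linearly to 1 at 2 h and stays flat. AUC(0–5) = 1 + 3 = 4 and AUC(5–6.5) = 1.5. The raw ratio is 1.5/4 = 0.375, an apparent fall. Per hour it is (1.5/1.5)/(4/5) = 1.25, an apparent rise. The sign depends on scaling, because 0–5 h includes the climb from zero.

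**4. C_max by hand, no heat effect.** Take 1 − exp(−kt) with an assumed half-life of 3 h. The value is 0.685 at 5 h and 0.777 at 6.5 h, a ratio of 0.777/0.685 = 1.13 before any assay or sampling noise.

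**5. Simulation, no heat effect.** There were 4,000 trials per setting with 12 subjects and the plan's sampling times. Assumptions: between-subject CV 30%, residual CV 5, 10 or 15%, linear trapezoid, and a two-sided 5% paired t-test on log ratios. The after/before C_max ratio is 5–6.5 h over 0–5 h.

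| Assumed profile | Mean ratio | False rise (nominal 2.5%) | False fall |
|---|---|---|---|
| Flat from 2 h | 1.02–1.05 | about 22% | about 0% |
| Rising, half-life 1–3 h, lag or depot 0–1 h | 1.07–1.38 | 86–100% | 0% |
| Peak at 4 h, then falling 5–10% per h | 0.92–1.05 | 0–25% | 0–100% |

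Counting the 5 h sample only as before heat lowers the false rise to about 12% (flat) and 68–100% (rising). It does not remove it.

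Over these profiles the AUC ratio was 0.38–0.71 raw, a fall in 100% of trials, and 1.25–2.37 per hour, a rise in 100%.

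The same-window heated/unheated ratio was 1.00 for both C_max and AUC, with two-sided rejection of 4–6% in every profile.

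**6. A second assumed model.** A one-compartment model with a 0.5 h lag, input half-life 1–4 h and elimination half-life 1.5–3 h, again without heat, gives C_max ratios of 1.18–1.48. Its AUC ratios are 0.71–1.02 raw and 2.4–3.4 per hour.

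**7. Product question, no heat effect.** The two products share a half-life (1 or 2 h) but differ in depot or lag by 0.5–1 h, with an assumed between-occasion CV of 15%. Comparing before/after C_max changes between the heated sessions gives a product ratio of 1.02–1.10 and a false product difference in about 7–79% of trials. The ratio of the two heated/unheated ratios gives 1.00 and about 5%.

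**8. Precision of the contrasts proposed below.** With s = √ln(1 + CV²) and t(0.975, 11 df) = 2.201, the 95% limits are the estimate ×/÷ exp(2.201 × s × √2/√12) for one heat ratio and ×/÷ exp(2.201 × s × 2/√12) for the ratio of ratios. For an assumed between-occasion CV of 15–25%, these factors are 1.14–1.25 and 1.21–1.37.

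**The case against.** The text never says that before and after are taken within one session. Read with Section 3.2, the phrase may be loose wording for with and without heat, and the studies cited alongside it may define it. The inter-procedure line already covers the heating interval, and the intra-procedure windows are also tabulated for the unheated sessions, so the time course would be visible. That makes this a fault of wording and designation, not of design. It does not settle which comparison is primary, and no rule requires the unheated sessions to be used as the correction.

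The plan names no test, so the false-positive rates belong to an assumed one. Section 5.2 treats the study as an estimation exercise, for which the bias is the better measure. For a flat profile that bias is only 2–5%. This stands. The profiles are also assumed: the direction of the C_max bias is not established, and the second model shows that a raw AUC fall is not inevitable.

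Between-session contrasts have costs too. They carry between-occasion variability and, if session order is fixed, period effects. The available text does not state the order and part of the document was not available, so no fault is asserted there.

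A window ending at 6 h 30 min could miss a delayed effect after the pad is removed. This is fair, but 5–6.5 h is the plan's own choice for the inter-procedure comparison, and a heated/unheated ratio over 6.5–9 h could be reported beside it.

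**Conclusion.** The concern holds. Taken as written, the comparison that Section 5.3 labels primary does not estimate a heat effect. Even a flat profile inflates the C_max ratio by 2–5%; rising profiles inflate it by 7–38%, and falling ones can reverse its sign. The AUC comparison is dominated by window length and by the initial climb from zero. These sizes rest on assumed profiles, residual CVs and a paired t-test, none of which the documents supply. The sample counts and window lengths come from the plan itself.

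The design can answer the question, because each product has an unheated session in the same subjects. What is missing is the designation of those pairs as primary and a written heat-by-product contrast. This should be fixed before analysis.

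**What to change.** In Section 5.3:

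- Make the primary heat effect the within-subject log ratio of heated to unheated session for the same product over 5–6.5 h, for C_max and AUC: Session 3/Session 1 and Session 4/Session 2.
- Make the product comparison the ratio of those two ratios.
- Report both with confidence intervals.
- Align the wording with Section 3.2.
- Keep the within-session windows descriptive, or report them relative to the unheated session's own before/after change.

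Optional additions are a mixed model with a random subject effect (and period, if session order varies) and a rule assigning each boundary sample to one window. Dividing AUC by window length helps display but does not remove the time effect.

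The cost is SAP wording and a small amount of analysis; the four sessions already supply the data. There are two drawbacks.

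- **Precision is limited.** With an assumed within-subject CV of 15–30% and n = 12, power to detect a heat ratio of 1.25 is 92% down to 40%. For a ratio of ratios of 1.25 it is 66% down to 22%. The product contrast should therefore be read from its interval.
- **Period effects.** If order is fixed from Session 1 to 4, each heat ratio spans two session steps. An assumed drift of 3% per session would add 1.03² − 1 = 6.1%. A log-linear drift cancels in the ratio of ratios, since (4 − 2) − (3 − 1) = 0.

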3 OBJECTIVES

3.1 Study Objectives

The present study aims to:

- 1) Determine serum rivastigmine concentrations after using Exelon® (matrix type TDS, Novartis Pharmaceuticals Corporation) and rivastigmine generic (matrix type TDS, Alvogen, Inc.) with and without standardized heat application in healthy adult subjects.
- 2) Determine residual drug content of TDSs for the purpose of estimating amount of drug absorbed.
- 3) Generate human PK data for the purpose of establishing an IVIVC model by collecting data following the application of rivastigmine products: Exelon® and rivastigmine generic TDS.

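### The IVIVC is meant for heat effect, but its three methods in 5.3 compare absolute levels; the heated/unheated ratio should be the main comparison, with the sources of CL and k stated

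*Combined protocol and SAP*

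**What the plan says.** Section 2.2 states the purpose: "The intent of this research is to establish an IVVC for the IVPT model in the specific context of heat effect studies". The intended use is to "evaluate whether all future generic products are similar in quality to the RLD in terms of heat effect".

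Section 5.3 lists three IVIVC methods:

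- Method 1: "The first method is to compare the steady state concentrations". The prediction is Css = Jss × A / CL, with the terms defined as "A=area; CL=clearance". No value or source for CL is given.
- Method 2 works by "predicting rivastigmine concentrations at each time point in the IVPT study and comparing it to the PK profile".
- Method 3: "The third method will be to determine and compare residual TDS analysis between in vitro and in vivo".

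Separately, 5.3 compares observed Cmax and AUC between time windows within a session, and between sessions over 5 h to 6 h 30 min. Those comparisons are in vivo only. They are not expressed as ratios and not tied to the in vitro permeation (IVPT) results.

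Two other parts bear on clearance. Section 3.1 includes the aim "Determine residual drug content of TDSs for the purpose of estimating amount of drug absorbed", and the non-compartmental analysis in 5.1 yields AUCinf and k.

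**The concern.** The question is whether IVPT predicts how much heat raises exposure, for each product and for one product relative to the other. None of the three methods compares that quantity in vitro and in vivo.

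An absolute comparison mixes two errors. One is a wrong heat effect, which matters for the stated purpose. The other is a constant scale error, from CL or from a fixed difference between flux through excised skin and flux in vivo. A scale error moves every predicted concentration, heated or not, and says nothing about heat. A model with the right heat effect can therefore agree worse than one with no heat effect at all, and the trial's own question is left without a direct answer.

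**Working it through.** **The plan's own figure.** Section 5.2 gives n = 12 and 82% power for AUC 166 ± 50 ng·h/mL and a 25% error. With two-sided 5%: n = (1.960 + 0.842)² × 50² / 41.5² = 11.4, so 12. Power = Φ(√12 × 41.5/50 − 1.960) = Φ(0.915) = 0.82. It reproduces and is not disputed, but it concerns absolute AUC. The plan gives no figure for the IVIVC.

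**Scale of Css.** The nominal 4.6 mg/24 h and AUC24h of 166 imply a rough apparent CL of 4600/166 = 27.7 L/h and an average of 166/24 = 6.9 ng/mL. Css is proportional to 1/CL. With CL 25% too low, 1/0.75 = 1.33 (+33%); with CL 25% too high, 1/1.25 = 0.80 (−20%). The ±25% is an assumption. A constant flux scale error multiplies Css in the same way.

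**Ratio at steady state.** (Jheat × A/CL) / (Jno heat × A/CL) = Jheat/Jno heat. A and CL cancel if heat does not change CL.

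**Ratio for the actual heat period.** Heat lasts 1.5 h from hour 5, so steady state does not apply. Take one compartment, constant flux for 9 h, and flux multiplied by R during 5 to 6.5 h. The documents give no R or half-life; assume R = 2 and half-life 1 to 3.5 h.

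- Cmax ratio over 5 to 6.5 h = 1 + (R − 1)(1 − e^(−1.5k)) / (1 − e^(−6.5k))
- AUC ratio over 5 to 6.5 h = 1 + (R − 1)[1.5 − (1 − e^(−1.5k))/k] / [1.5 − (e^(−5k) − e^(−6.5k))/k]
- AUC0-12 ratio = 1 + (R − 1)E/B, with B = 9 − (e^(−3k) − e^(−12k))/k and E = 1.5 − (e^(−5.5k) − e^(−7k))/k

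| Half-life | Cmax ratio, 5 to 6.5 h | AUC ratio, 5 to 6.5 h | AUC0-12 ratio |
|---|---|---|---|
| 1 h | 1.654 | 1.386 | 1.168 |
| 2 h | 1.453 | 1.255 | 1.165 |
| 3.5 h | 1.355 | 1.199 | 1.159 |

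Volume V appears in none of these, so with k fixed a CL error cancels exactly. With V fixed, a CL error changes k:

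- Half-life 1 h: Cmax ratio 1.654 becomes 1.561 (CL −25%) or 1.730 (CL +25%), that is −5.6% or +4.6%.
- Half-life 3.5 h: 1.355 becomes 1.323 or 1.388, that is −2.4% or +2.4%.

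**Two imperfect models compared, R = 2.**

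- No heat effect, all else right: heated AUC0-12 is under-predicted by 1 − 1/1.168 = 14.4% (half-life 1 h) to 1 − 1/1.159 = 13.7% (3.5 h).
- Right heat effect, CL 25% too low: every concentration is 33% too high with k fixed. With V fixed, heated AUC0-12 is proportional to (B + E)/k. It goes from 14.86 to 19.31 at half-life 1 h (+30%) and from 39.1 to 45.3 at 3.5 h (+16%).

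On absolute AUC0-12 the first model looks better throughout. On the 5 to 6.5 h ratio it predicts 1.00 where the true values are 1.36 to 1.65 (Cmax) and 1.20 to 1.39 (AUC). The second model is exact with k fixed and within about 6% on Cmax with V fixed.

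**Method 3.** Doubling the nominal flux for 1.5 h releases a further 4.6 × 1.5/24 = 0.29 mg, which is 3.2% of the 9 mg load and 4.2% of the 6.9 mg load. That is a small signal in an absolute residual.

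**Clearance from within the study.** Amount absorbed divided by AUCinf gives an apparent CL. Nominal absorption over 9 h is 4.6 × 9/24 = 1.725 mg. A 5% error in drug content is then 0.45/1.725 = 26% of the absorbed amount for Exelon and 0.345/1.725 = 20% for the generic. For half-lives of 1 to 3.5 h, about 2% to 26% of AUCinf lies beyond the last sample at 12 h.

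**The case against.** A reader might infer that CL cannot be obtained without an intravenous arm and must come from outside. The documents do not support that: residual drug with AUCinf gives an apparent CL. It is imprecise, assumes that all drug lost from the system is absorbed, and is partly circular if it is then used to predict the same serum data. What stands is that 5.3 does not say which CL will be used.

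A reader might also infer that the ratio is immune to clearance. That is exact only at steady state or with k fixed. With V fixed, the heat effect itself (ratio minus 1) still moves by about 9% to 17% in relative terms for a 25% CL error.

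Nor is Method 2 blind to heat. Of 20 post-application samples, 7 fall in 5 h to 6 h 30 min, and a model without heat would misfit there: it would under-predict Cmax in that window by 1 − 1/1.355 = 26% to 1 − 1/1.654 = 40%. But 5.3 does not direct the comparison to that window or separate heat from scale.

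Section 5.3 sets no acceptance criterion, and developing a correlation may include a scale factor. That a sound model will be declared a failure is therefore not something the plan implies.

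Finally, 5.3 already predicts PK parameters and names Cmax and AUC before and after heat as primary, so the ratios could be formed later. This is true, and it makes the change cheap. It does not make the ratio part of the planned IVIVC.

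**Conclusion.** The point holds in this form: the IVIVC methods do not directly compare the quantity they are meant to validate, and the concentration methods rest on a CL of unstated source. A CL error assumed at ±25% moves predicted Css by +33% to −20% in all sessions. The same error moves the 5 to 6.5 h Cmax heat ratio by 0% (k fixed) or about −6% to +5% (V fixed), while missing heat altogether costs only about 14% on heated AUC0-12.

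These sizes rest on assumed values: one compartment, R = 2, half-life 1 to 3.5 h. With R = 1.5 the AUC0-12 ratio is 1.08 and the miss only 7% to 8%, so absolute agreement discriminates even less; a larger heat effect would be easier to see. That no CL source is given is judged on the text available, from which some material had been removed. The data collected are not at risk. The weakness lies in how the IVIVC would be judged.

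**What to change.** In 5.3:

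1. Make the main IVIVC comparison the predicted versus observed heated/unheated ratio of AUC and Cmax over 5 h to 6 h 30 min, for each product: Session 3/Session 1 and Session 4/Session 2.
2. Take the predicted ratio from Method 2 concentration profiles for heated and unheated IVPT, with a stated k. A raw flux ratio will not do: in 1.5 h, serum covers only 1 − e^(−1.5k) of the way to its new level, or 65% to 26% for half-lives of 1 to 3.5 h.
3. Then compare the predicted and observed generic/RLD ratio of these heat ratios.
4. State the sources of CL and k. If either comes from this study's own data, say so and note the circularity.
5. Keep the three absolute comparisons as secondary.

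The cost is a few sentences and some ratios from data already planned, with no extra subjects or samples. The downside is small: a ratio does not validate absolute level, which is why the existing methods stay, and it still depends on k, so results should be shown over a plausible range of k.

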5.2 Sample Size Considerations

To calculate the sample size required to achieve an 80% power, we considered a parameter estimate (area under the curve (AUC)) with a maximum error within 25% of the reported value to be acceptable. The sample size calculation used was reported by Panetta et al. and is as follows ⁽⁹⁾:

$$n = \frac{(Z_{\alpha} + Z_{\beta})^2 * \zeta^2}{\epsilon^2}$$

where n represents the sample size required, Z_{α} represents the z score for the type 1 error, Z_{β} represents the z score for the type 2 error, ζ represents the standard deviation of the parameter and ϵ represents the predicted error of the parameter estimate. The type 1 error was fixed to 5% and the type 2 error was fixed to 20%.

For Exelon[®], assuming a mean \pm SD AUC_{24h} of 166 ± 50 ng*h/mL (30% CV), the sample size calculations using the above formula indicated that $n=12$ subjects would provide a power of 82% for a predicted error of 25% on the AUC ⁽⁸⁾.

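### Section 5.3 makes pre- versus post-heat AUC primary, but its within-session windows of unequal length cannot show a heat effect, and the valid same-product between-session contrast is planned without being named as the primary result

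*Combined protocol and SAP*

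**What the plan says.** Section 5.3 lists the primary comparisons as Cmax "before and after heat application; 2) AUC before and after heat application consistent with similar PK studies". It then gives two sets of comparisons.

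- **Intra-procedure, Sessions 1-4.** "AUC: will be compared among the following time periods: 0-5 h, 5 h-6 h 30 min, 6 h 30 min-9 h", followed by a last window of 9-12 h.
- **Inter-procedure, Sessions 1-4.** Cmax and "AUC will be compared among procedure groups for the following time periods: 5 h -6 h 30 min".

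Three other places bear on how these are read.

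- The Protocol Summary (Description of Study Design) has heat "applied for 1 hour 30 minutes at 5 h after application of the TDS" in Sessions 3 and 4 only, that is from 5 h to 6.5 h. The TDS is worn for about 9 h in every session. Sessions 1 and 3 use Exelon; Sessions 2 and 4 use the generic.
- Section 3.2 gives the outcome as "area under the curve (AUC) attained with and without heating for Exelon" and the generic, without naming a window or a session pair.
- Section 5.1 specifies the linear trapezoidal rule and sampling that ends with "10 h, 11 h and 12 h post-TDS application". It does not mention dividing AUC by window length.

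**The concern.** AUC grows with the length of the interval over which it is taken. Comparing undivided AUC among windows of 5, 1.5, 2.5 and 3 h therefore mixes any heat effect with window length. It also mixes it with time since application: drug is still accumulating after a first application, and the last window falls after removal of the TDS.

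The before-and-after wording of the primary comparison fits the within-session rule most readily, because no other rule in Section 5.3 has a before and an after period. The comparison that does isolate heat is in the same section, but it is not ranked and its session pairs are not named. An analyst could follow either rule, or choose between them after seeing the data, and the two can point in opposite directions. The effect of heat on each product is the main purpose of the study, so the plan should say which contrast carries the conclusion.

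**Working it through.** **The plan's own figure first.** Section 5.2 uses n = (Zα + Zβ)² × SD² / error². "The type 1 error was fixed to 5% and the type 2 error was fixed to 20"%. Sidedness is not stated. With a two-sided 5% level, 30% CV and 25% error, n = (1.960 + 0.842)² × 0.30² / 0.25² = 11.30, rounded up to 12. Power at n = 12 is Φ(√12 × 0.25/0.30 − 1.960) = Φ(0.927) = 82.3%, which matches the stated 82%. A one-sided level gives n = 9 and 89%, which does not match. The calculation concerns one 24 h AUC, not a heat contrast, so nothing below changes it.

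**Step 1: window lengths (Section 5.3).** 5 − 0 = 5 h; 6.5 − 5 = 1.5 h; 9 − 6.5 = 2.5 h; 12 − 9 = 3 h.

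**Step 2: flat profile, no heat effect, no kinetic model.** AUC = concentration × length, so the four AUCs stand at 5 : 1.5 : 2.5 : 3.

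- During/before = 1.5/5 = 0.30, an apparent fall.
- After/during = 2.5/1.5 = 1.67, an apparent rise.
- Mean concentration at 5-6.5 h must exceed 5/1.5 = 3.33 times the 0-5 h mean before undivided AUC rises at all.

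**Step 3: rising profile after a first application.** The documents give no half-life, skin-depot rate, lag or size of heat effect, so all of these are assumptions. Each model has constant input until 9 h, a first-order skin depot and one-compartment elimination. AUC is taken by the linear trapezoidal rule at the 21 sampling times of Section 5.1, with the pre-dose sample set at 0 h. The ratio is AUC(5-6.5 h)/AUC(0-5 h) within one session.

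| Assumed kinetics | No heat | Heat doubles the rate |
|---|---|---|
| A: no lag; depot half-life 0, 0.5, 1 h; elimination half-life 1 to 4 h (15 cases) | 0.43-0.74 | 0.58-0.79 |
| B: as A, with 1 h lag and depot half-life up to 2 h | 0.51-1.14 | 0.71-1.21 |
| C: lag 0-1 h; depot rate 0.3-1.0/h; elimination rate 0.2-0.46/h | 0.57-1.15 | 0.76-1.54 |

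In A and B heat doubles input over 5-6.5 h. In C it also doubles release from the depot. Without heat the ratio already falls on both sides of 1, and the no-heat and heated ranges overlap in every row.

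**Step 4: dividing by window length.** This multiplies each ratio by 5/1.5 = 3.33. The no-heat ratio becomes 1.43-2.47 in A and 1.91-3.83 in C. A steep rise remains with no heat effect, because concentration is still climbing.

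**Step 5: same window, heated over unheated session, same product.** With no heat effect the ratio is 1.00 in every case, since length and accumulation cancel. With the doubling, 5-6.5 h gives 1.07-1.38 in A and 1.22-1.43 in C. Later windows in A give 1.22-1.37 (6.5-9 h), 1.11-1.21 (9-12 h) and 1.19-1.28 (5-12 h).

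**Step 6: which session pairs isolate heat.** Four sessions give 4 × 3/2 = 6 pairs. Two differ only in heat (3 vs 1, 4 vs 2), two only in product (1 vs 2, 3 vs 4), and two in both (1 vs 4, 2 vs 3).

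**Step 7: how much of the heat effect falls inside 5-6.5 h.** Share = (heated − unheated AUC at 5-6.5 h) / (the same difference over 5-12 h). In A this is 6-38%.

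**The case against.** The strongest reply is that the valid contrast is already in the plan. Section 5.3 compares sessions over exactly the heating period, and the Section 3.2 wording, with and without heating for each product, implies Session 3 vs 1 and Session 4 vs 2. The intra-procedure list covers all four sessions, two of them unheated, so it need not be a test of heat. The unheated sessions can show the pattern to expect without heat. No hypothesis test or decision rule is attached to the within-session ratio. This stands: it limits the point to ranking, pairing and interpretation. It does not remove the point, because Section 5.3 never states the cross-session reading of those windows or says which comparison delivers the primary result.

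A second reply concerns size. A reader might infer from row A that a heated session will always show a lower AUC during heat than before it, or that a several-fold rise in input is needed to reverse this. Neither holds in general. With a lag and a slower depot the ratio can exceed 1 even without heat. The flat profile is also not realistic for a first application; it shows only the effect of window length.

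A third reply is that making 5-6.5 h primary sits awkwardly with the finding that much of the heat effect may come later. That is fair. The window is kept because it is the one already planned between sessions, and the later windows are added beside it. Whole-session AUC, available under Sections 3.2 and 5.1, could capture later exposure, but Section 5.3 does not list that contrast.

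**Conclusion.** The point holds and should be fixed. The within-session AUC comparison cannot show a heat effect: with no heat effect, during/before is 0.30 for a flat profile and about 0.4 to 1.15 under the assumed first-application kinetics. The error can go in either direction. Window lengths and the flat-profile ratios follow from the text alone. The wider range and the 6-38% share rest on the assumed half-lives, depot, lag and doubling, and should not be quoted as the expected size in this trial. That AUC is undivided is inferred from the absence of any stated normalisation. The no-heat ratio of 1 between sessions assumes that paired sessions differ only in heat.

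A reader might conclude that the trial has no valid heat analysis, or that the 5-6.5 h comparison between sessions is itself distorted by window length. The documents support neither. That comparison is planned and sound. Its gaps are that it is not named as primary, not paired by product, and covers only heat-related exposure that reaches serum before heating ends.

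**What to change.** In Section 5.3:

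1. Label the intra-procedure AUC comparison as descriptive and report it per hour. The per-hour scale helps presentation but does not remove accumulation.
2. State that the primary AUC conclusion on heat is the within-subject, same-product, same-window contrast at the already planned 5-6.5 h: Session 3 vs 1 for Exelon and Session 4 vs 2 for the generic.
3. Report the same contrast for 6.5-9 h and 9-12 h, or for 5-12 h, as supportive, since heat-related exposure can reach serum after heating ends.

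The cost is a wording change and a few extra contrasts on data already collected, with the same samples and NCA software. Design, sample size and stated power do not change.
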